5.1.2 Diabetes Inclusion Criteria ^[69,25]

Only patients with type 2 diabetes will be enrolled in this study.

1. Random blood glucose greater than 200mg/dL
2. Hemoglobin A1C greater than 6.5%
3. Use of hypoglycemic agents except Metformin or
4. Type 2 diabetes included in problem list

Figure 5.1.2 summarizes identification Diabetes candidate pool

5.1.3 Hypertension Inclusion Criteria [65]

1. Systolic blood pressure greater than 140mmHg on two different occasions at least one week apart
2. Diastolic blood pressure greater than 90 on two occasions at least more than one week apart
3. Use of antihypertensive agents except thiazide diuretics or
4. Hypertension included in problem list

Figure 5.1.3 summarizes identification Hypertension candidate pool

[figure not shown]

Figure 5.1.1 Identification CKD Candidate Pool

[figure not shown]

Figure 5.1.2 Identification Diabetes Candidate Pool

[figure not shown]

Figure 5.1.3 Identification Hypertension Candidate Pool

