5.1 Subject Inclusion Criteria

In order to participate in the study, patients should be 18-85 years of age and have coexistent CKD, type 2 diabetes and hypertension.

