6.5 Implementation Collaborative Model of Care

The interventions selected for this pragmatic trial are supported by prior studies, clinical evidence and/or guidelines for treatment of CKD, diabetes and hypertension.^[5,25,24,65,67-71,31,34,11] Specific interventions include maintaining blood pressure less than 140/90mmHg, use of angiotensin-converting enzyme inhibitors (ACEI) or angiotensin receptor blockers (ARB), treatment with statins, aiming for hemoglobin A1C at the recommended target for coexisting

comorbidities, and avoiding nephrotoxic medications including non-steroidal anti-inflammatory drugs (NSAIDS). Other interventions will include education on CKD for both primary care providers and for patients using material prepared by NKDEP. Material on lifestyle modification and immunizations will also be included. (see figure 6.5.1)

After a patient is enrolled, the primary care practitioner activates the CKD, diabetes and hypertension collaborative model of care. The primary care practitioner will also have the option to activate smart forms already constructed and available from our team (see appendix section) from the electronic health record. Primary care practitioners will have the option to initiate protocols for CKD management, hypertension management, lipid and diabetes management. Protocols can be initiated via smartsets in the EHR. (see figures 6.5.2 *Initiation of Protocol from SmartSets and Links to SmartSets*). The specific and detailed protocols for hypertension management and diabetes/lipid management are included in appendices.

ICD-Pieces Patient Care Work Flow

[figure not shown]

Figure 6.5.1

Initiate Protocol from SmartSets

- From the SmartSet, the provider can place all 3 initiate orders at once, in a Future status

[figure not shown]

Figure 6.5.2 Initiation of Protocol from SmartSets

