7.1 Screening

Potential study participants from each healthcare system followed in primary care clinics randomized to the study will be screened for inclusion according to the pre-established criteria for CKD, diabetes and hypertension (see section 5.1) and as illustrated in figure 6.3.1

There are no plans to obtain individual informed consent for patients screened or randomized in the study. (see section 14.3) Information about the study will be available to all patients in participating clinics and who have the triad of CKD, diabetes and hypertension. There will be an opt-out opportunity from the interventions or from use of information from any patient who requests their data not to be used for analysis.

Screening of participants will occur at an initial stage to identify a candidate cohort of patients in various eligible clinics (see figure 6.3.2). Patients who do not fulfill required diagnostic criteria on initial review and require a separate determination to confirm any of the three diagnosis will be rescreened at the time of a future visit (figure 6.3.3)

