Appendix I: CHRONIC KIDNEY DISEASE (CKD) HYPERTENSION MANAGEMENT PROTOCOL

This protocol will be initiated as directed by CHRONIC KIDNEY DISEASE (CKD) CHRONIC DISEASE MANAGEMENT PROTOCOL.

Protocol will be reviewed every year.

RN will perform protocol with assistance from PA or NP at same clinical site.

PA or NP may suggest deviations from protocol as deemed clinically appropriate.

Orders (except medication orders) will be placed by RN in electronic medical record using "per protocol" order mode with physician, PA or NP as authorizing provider. Medication orders may be routed to provider as suggested per protocol, but medication and dose will ultimately be selected and ordered by provider. After medication orders are finalized by provider, RN will notify patient of final decision.

Goals/Background

1. Chronic Kidney Disease (CKD) is defined as (for the purposes of this protocol):
 - a. Glomerular Filtration Rate (GFR) < 60 mL/min
 - b. Or presence of proteinuria, defined as any one of the following:
 - i. Random Urine Protein/Creatinine Ratio > 200 mg/g
 - ii. Random Urine Microalbumin/Creatinine Ratio > 30 mg/g
 - iii. 24 hour Urine Protein > 150mg
 - iv. Urine dipstick protein (adjusted for specific gravity)
2. Blood pressure (BP) goals
 - a. For patients with CKD goal blood pressure is Systolic (SBP) < 140 mmHg AND Diastolic (DBP) < 90 mmHg
3. ACEi/ARB
 - a. All patients with chronic kidney disease (with or without proteinuria) should be treated with an angiotensin converting enzyme inhibitor (ACEi) or angiotensin receptor blocker (ARB).
 - b. Recommended ACEi: lisinopril
 - i. Starting dose 5mg once daily if GFR > 10 mL/min or 2.5mg if GFR < 10mL/min
 - ii. Maximum dose 40mg once daily
 - iii. Class-specific considerations. Be aware of these potential adverse effects when conduction follow-up of initiation or titration of this medication (details on the follow-up process are below).
 1. Elevated potassium (hyperkalemia)
 2. Reduction in kidney function (increase in creatinine or decrease in GFR)
 3. Dry cough

- 4. Facial swelling (angioedema)
- c. Recommended ARB: losartan
 - i. Starting dose 25mg once daily
 - ii. Maximum dose 100mg once daily
 - iii. Class-specific considerations. Be aware of these potential adverse effects when conduction follow-up of initiation or titration of this medication (details on the follow-up process are below).
 - 1. Hyperkalemia

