viii. RN Blood Pressure Assessment: Ask patient about missed doses of BP medications in last 24 hours. If any missed doses, reschedule BP measurement 1-2 weeks after improved adherence. Ask patient about use of nicotine products. Wait 30 minutes after last use before measuring blood pressure. Measure and record blood pressure according to JNC 8 standards: After patient has sat quietly for 5 minutes in chair, measure with arm supported at heart level and with legs uncrossed and feet on the floor. Obtain at least two measurements and record the average of the two —sum of systolic values divided by 2 and sum of diastolic values divided by 2. (See Page number 4 (which is page 20 of 52 including introductory section) of the following link for full details:
<http://www.nhibi.nih.gov/guidelines/hypertension/express.bdf>).

1. "RN BP measurement" below refers to average calculated as above per JNC 8 guidelines.
2. If patient does not have written home blood pressure log and RN BP measurement is > 140 mmHg systolic or > 90 mmHg diastolic, initiate CKD HYPERTENSION PROTOCOL and perform at this visit.
3. If patient does not have written home blood pressure log, and RN BP measurement systolic < 140 mmHg AND diastolic < 90 mmHg, no further action is necessary.
4. Home Blood Pressure Device Validation
 - a If patient provides written home blood pressure log, review documentation in overview section of CKD diagnosis in problem list for date of last blood pressure device validation.

- i. If validation in < 1 year, proceed to "Home Blood Pressure Log Review".
- ii. If no validation in > 1 year and patient did not bring home blood pressure device, then schedule follow-up appointment in 1-2 weeks with RN. Ask patient to provide new written blood pressure log and bring home blood pressure device to appointment for comparison with RN measurement.
- iii. If no validation in > 1 year and patient brings home blood pressure device, obtain measurement from home blood pressure device.
 - 1. Ask patient to demonstrate proper use of device and provide education as needed according to JNC 8 guidelines above.
 - 2. If difference > 10 mmHg (systolic or diastolic) between home device and RN measurement, disregard home blood pressure log and notify patient that device is not sufficiently accurate. a. Under CKD diagnosis in Problem List, record in Overview section: "Home BP Device Validation [DATE]: home device not consistent with RN measurement."

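### Hypertension criterion 3 lets ACEi/ARB use alone stand for hypertension in CKD patients, and the prescription need not predate randomisation

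*Combined protocol and SAP*

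**What the plan says.** Section 5.1 requires that "patients should be 18-85 years of age and have coexistent CKD, type 2 diabetes and hypertension". Section 5.1.3 then gives four ways to establish hypertension: repeated high systolic readings, repeated high diastolic readings, drug use, or a problem-list entry. The drug item reads "Use of antihypertensive agents except thiazide diuretics or", followed by "Hypertension included in problem list". Thiazides are the only class excepted.

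Appendix I, under Goals/Background, says: "All patients with chronic kidney disease (with or without proteinuria) should be treated with an angiotensin converting enzyme inhibitor", or alternatively an ARB. No BP condition is attached. Section 6.5 lists ACEI/ARB use as an intervention separate from the BP target. The stepwise part of Appendix I, however, depends on BP. With systolic below 140 and "diastolic < 90 mmHg, no further action is necessary".

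On timing, Section 4 plans two years of recruitment, Section 5.4 states that intervention sites are not masked, and Section 6.4 has Pieces confirm eligibility within clinics already randomised to intervention. Section 7.1 adds a later look: candidates that "do not fulfill required diagnostic criteria on initial review and require a separate determination to confirm any of the three diagnosis will be rescreened" when they next attend.

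**The concern.** The criterion is meant to identify hypertension, but for one drug class it cannot separate hypertension from kidney protection. CKD is an entry requirement, so every patient being screened belongs to the group for whom the protocol's own Goals recommend that class.

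Two things are at stake. The first is who is in the trial: some enrolled patients may lack the third condition, leaving the BP component little to act on. The second is comparability. In an open-label cluster trial with rolling enrolment, an entry criterion that can be met by a prescription written after randomisation, for a drug the intervention encourages, can admit different patients in the two arms.

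**Working it through.** **1. Is drug use sufficient alone?** The items in 5.1.3 end with a single 'or' before the last, the same pattern as the diabetes list in 5.1.2. Read cumulatively, the list would demand high systolic readings, high diastolic readings and drug use together, which is implausible. Read as alternatives, criterion 3 suffices.

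**2. Does another step catch a normotensive ACEi/ARB user?**
- Rescreening in 7.1 is for patients who do not meet criteria, so someone meeting criterion 3 is not sent there.
- The medication review in 15.2 checks that drug codes map to the intended drug and route, not why the drug was prescribed.
- Thiazides (5.1.3) and metformin (5.1.2) are excepted, so excepting a drug is an accepted device, but no reason is given for leaving ACEi/ARB in.

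**3. Can the criterion be met after randomisation?** Under 6.4, candidates are found first and practices are then randomised. Patients who already qualified at that point raise no between-arm problem. Those confirmed later, during two years of open-label recruitment, might. In the pilot (Section 2.2.3, n=107), ACEi/ARB use rose from 57.8% at screening to 87.2% at last follow-up. That shows the care model is associated with more use. It has no control group, and the hypertension status of the users is not given.

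**4. The plan's own sample size (Section 11.2).** Inputs: 14% against 11%, ICC 0.015, 80% power, two-sided 5%; available patients 4,419, 4,738, 4,175 and 1,093 in 25, 40, 50 and 9 clinics. I assume 1:1 allocation, since no ratio is stated.
- Unclustered total, pooled-variance formula: 2 × [1.96√(2p̄q̄) + 0.8416√(p₁q₁ + p₂q₂)]² / 0.03², with p̄ = 0.125, which gives 3,813, or 3,814 when each arm is rounded up to 1,907.
- Patients per clinic, m: 176.8, 118.5, 83.5, 121.4. Design effects 1 + (m − 1) × 0.015: 3.64, 2.76, 2.24, 2.81. Weighted by patients: 2.881.
- N = 3,813 to 3,814 × 2.881 = 10,987 to 10,990, against 10,991 stated. The figure reproduces, and power at 10,991 is 80.0%.

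**5. Dilution, illustration only.** Let q be the share qualifying by criterion 3 alone and truly without hypertension, and k the fraction of the effect they lose. The difference becomes 3.0 × (1 − kq) points. Effective size per arm is 10,991 / 2 / 2.881 = 1,907. Both q and k are assumptions; the control rate is held at 14%.

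| q | k = 0.5: difference, power | k = 1: difference, power |
|---|---|---|
| 5% | 2.93 points, 77.9% | 2.85 points, 75.6% |
| 10% | 2.85 points, 75.6% | 2.70 points, 70.8% |
| 15% | 2.78 points, 73.3% | 2.55 points, 65.7% |

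If these patients instead have half the event rate (7%) and the same relative reduction, power is 78.9% at q = 5% and 77.7% at q = 10%. If they have the same event rate and the same benefit, it stays at 80%.

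**6. Differential entry, illustration only.** Suppose the intervention arm gains an extra 5% of patients through new ACEi/ARB use, at a 7% event rate rather than 14% (both assumed). With no treatment effect, its rate is (14 + 0.05 × 7) / 1.05 = 13.67%, a spurious difference of 0.33 points, or 0.33 / 3.0 = 11% of the planned effect.

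**The case against.** The strongest reply is that the sequence in the protocol works against selection by arm. The care model is activated after enrolment (6.5), and order sets are triggered for enrolled patients (6.3). An unconfirmed candidate is flagged for confirmatory testing, not for a drug (15.2). Educational resources go to all practitioners (5.3), and both groups have access to recommended therapies (14.3). This largely stands. It leaves only an indirect route: changed prescribing by clinicians in intervention practices to candidates not yet enrolled. Section 15.2 also specifies identical query logic on local data copies, but the same query can read records that prescribing in one arm has altered.

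Second, a drug-only patient can still benefit from statins, glycaemic targets, nephrotoxin avoidance, education and the ACEi/ARB itself, and the 3-point effect may already describe a population chosen by these rules. That stands too, and is why the dilution figures are illustrations.

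Third, the operative definition is not fully visible: Figure 5.1.3 is not shown, and the medication target list mentioned in 15.2 is not in the text.

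Three stronger readings are tempting and not supported:
- A reader might infer that the protocol also recommends beta-blockers after infarction or in heart failure, or loop diuretics, regardless of BP. It does not. Those steps follow a BP above goal, and each protocol asks again whether BP is at goal.
- A reader might infer that the trial creates eligibility in the intervention arm. The documents show only that it could.
- A reader might infer that 10,991 is wrong. It reproduces.

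**Conclusion.** The point holds as a gap in the definition and its timing. As written, a normotensive patient with CKD and type 2 diabetes on an ACEi or ARB can satisfy criterion 3, and nothing in the text limits that to prescriptions made before randomisation. Entry of such patients is possible; how many is unknown. Different entry by arm is plausible but not demonstrated. The losses of power in step 5 and the 0.33-point bias in step 6 rest wholly on assumed inputs and should not be quoted as estimates.

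It is worth correcting because the remedy is cheap and the calculated power is 80% with no reserve. It does not undermine the design.

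Separately, Appendix I is not consistent with itself: its Goals recommend ACEi/ARB for all CKD patients, while its algorithm takes no further action when BP is below goal. The sponsor must reconcile the two. No view is taken here on which is right.

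**What to change.** 1. In 5.1.3, count ACEi/ARB use under criterion 3 only when the prescription predates the practice's randomisation, and state that the same query runs in both arms.
2. Report, by arm, how many patients qualified on criterion 3 alone.
3. In 11.3, add a sensitivity analysis of the primary outcome excluding those patients. With the date limit in place, membership of this group through an ACEi/ARB rests on a prescription made before randomisation.
4. Reconcile the Appendix I Goals statement with its BP-dependent algorithm.

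The cost is one change to the Pieces query and some added reporting. Section 15.2 already stores snapshots of the data elements used for identification and confirmation, so the counts should be obtainable without new data collection. The small downside is that a few patients first treated after randomisation must qualify through BP readings or the problem list.

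The date limit deals with differential entry. It does not remove normotensive patients already on the drug, which is what the count and the sensitivity analysis are for. Requiring a diagnosis code or a high reading alongside drug use would go further, but I do not ask for it: it would drop treated, controlled hypertensives without a coded diagnosis, and the trial already needs 76.2% of its identified pool (10,991 of 14,425).

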5.2 Subject Exclusion Criteria

All eligible patients from clinics randomized to the study will be included in the comparison of the two groups regardless of intervention compliance (intention-to-treat analysis).

Exclusion criteria will be minimal in this pragmatic trial. The collaborative model of care will not be implemented in patients younger than 18 years or older than 85 years of age or patients who have CKD stage 5/ERSD. Primary care practitioners have the option of not implementing the intervention on any of their patients if they believe benefit to be minimal or risk too high due to patient comorbidities. Patients also have the option to opt-out from the facilitated collaborative model of care.

5.3 Strategies for Recruitment and Retention

Prior to initiation of the study there will be information materials and education sessions provided to all participating sites. This will include both written material and electronic information. Resources from National Kidney Disease Education Program (NKDEP) will be provided to all practitioners.^[82] There will also be special attention to selection of study champions at each participating site. In addition, there will be plans to visit most of the participating healthcare sites by members of the study team. These efforts will continue not only early in the study but throughout the study to promote study retention.

Participating healthcare systems will be provided with advance notice of possible study participants prior to upcoming appointments.

There will be review of actual enrollment of patients versus enrollment goals for every participating site. Reviews will occur monthly and reported quarterly.

5.4 Treatment Assignment Procedures

This is a prospective stratified cluster randomized trial. Primary care practices will be stratified by healthcare system and randomly allocated to active intervention or control using standard

medical care using a randomized permutation block within stratum. There will be no masking of sites randomized to active intervention.

Practitioners and/or patients can choose to withdraw for the study at any time. They can choose not to follow the intervention model (any or all of the components or tools of care). Patient can request their data be not included for analysis of outcomes.

The study can be terminated by the DSMB for various reasons including concerns about adherence to protocols, study enrollment or patient safety.

6. Study Interventions

6.1 Healthcare System Collaboratory

The pragmatic trial ICD Pieces is part of the NIH Collaboratory for Healthcare Systems Research with a special emphasis on multiple chronic conditions. The study will be conducted by a collaborative network of UT Southwestern and several other cores and four large healthcare systems that provide care to more than 2.5 million patients. (see *figure 6.1*)

ICD-Pieces Pragmatic Trial Organization

[figure not shown]

Figure 6.1

The University of Texas Southwestern Medical Center is the central academic partner for this collaborative and has a strong commitment to both patient care and research. Parkland Health and Hospital System is an integrated healthcare system that serves as a safety net hospital for the underserved and uninsured residents of Dallas County. Texas Health Resources is one of the largest non-profit health systems in the United States serving a population close to 1 million individuals in North Central Texas. The Veterans Administration Healthcare System is the largest integrated health care system in the United States and the largest provider of care for patients with CKD in the country. The North Texas VA Healthcare System serves more than 100,000 patients in North Texas. Pro Health Physicians of Connecticut is one of the largest healthcare providers in Connecticut providing care to more than 250,000 adults every year across multiple practices.

6.2 Informatics Architecture

Pieces will be deployed through the cloud to the participating healthcare systems. (see *figure 6.2.1*) The Parkland Center for Clinical Innovation will provide specifications for data extraction using batch files and the data from each hospital will be mapped to relevant fields in the electronic health records systems. The Pieces system will access electronic health records for all patients who receive care at the participating sites for the study and to specifically detect patients with a triad of CKD, diabetes and hypertension and to detect eligible participants, facilitate management and monitor outcomes. Each healthcare system will have some differences in their electronic health records and data flow. This is being addressed with backup systems in place to access data and allow for safe and secure transmission. The North Texas VA will not be transmitting patient specific information via the cloud at least in the early stages of the trial. Data from each site will be programmed to be de-identified in the cloud and sent securely to the Biostatistics and Research Design Core at UT Southwestern. Please see *figure 6.2.2* for a model of information flow based on deployment of Pieces at participating sites of the

healthcare systems in the study. Section 15 Data Handling and Record Keeping provides additional details on data capture and transmission

Study Sites

Pieces™ Connects with Implementation Sites

Figure 6.2.1

[figure not shown]

Figure 6.2.2

6.3 Practice Facilitator

A key component of the collaborative model of care for the intervention group is the introduction of practice facilitators. In order to maximize the successful implementation of care in the intervention group the role training of the practice facilitator will be standardized across sites. We will use a curriculum developed following principles detailed in the Practice Facilitation Handbook from the Agency for Healthcare Research and Quality and especially adapted for ICD-PIECES.^[89] We have two content experts that will lead these efforts. [name] from NIDDK has developed educational programs which have been successfully used by NKDEP to successfully train healthcare professionals to care for thousands of patients who have CKD, diabetes and hypertension. [name] from SUNY directs a training program at SUNY for practice facilitators working in primary care practices.

There will be an initial on-site course for practice facilitators led by [name] and [name]. After that initial meeting ICD-PIECES will continue to provide scheduled events by teleconference, written material and webinars to disseminate study relevant material to practice facilitators. All practice facilitators will also participate in regularly scheduled calls to review study progress. It is anticipated that these call will be at least weekly early in the study with additional calls and site visits to each site over the duration of the study.

Practice facilitators may defer in professional qualifications among the different healthcare sites. Practice facilitators will have some clearly defined responsibilities including the following:

- Receive initial and on-going training from the study team about the study, study protocol and proposed intervention
- Ensure training of designated clinic staff on clinic level activities and expectations
- Ensure necessary participation of designated clinic staff in CKD, diabetes, and hypertension care

- Coordinates with study clinic staff to ensure the following activities:
 - List of eligible patients scheduled for clinic visit weekly are received through the EHR weekly
 - Site-specific enrollment protocol are activated for eligible patients
 - Smart/Order set in the EHR are triggered for enrolled patients
 - Holds weekly conference calls with clinic representatives to answer any questions and monitor enrollment number for each clinic
- In-person visit to observe processes of enrollment and Smart/Order set trigger and other intervention activities
- Provides regular update to the site PI and monthly update to the study team on enrollment number, performance of study clinic and on-going challenges

